9.2.10 Patient Impression of Change Questionnaire (PICQ)

On Day 28 and on Day 60, the patient will be asked to complete a PICQ. It collects the patient's impression on how his/her overall status has changed from baseline. A copy can be found in section 17.3 of this protocol.

9.2.11 Concomitant treatment

Medications will not be altered for the purpose of this trial, however, any medication changes during screening must be recorded, as must those started before randomization and continued thereafter. At each study assessment, changes in concomitant treatment must be recorded. To allow for accurate information about all medication a patient was

taking at the moment an (S)AE occurred, stop and start dates of concomitant medications must be recorded throughout the study.

Because CardiolRx™ is known to inhibit the metabolism of certain other drugs, new symptoms or findings may represent toxicity from a concomitant medication that had previously been well tolerated. For more detailed discussion of DDIs, see the IB, Section 6.3.

In addition, to aid investigators in screening concomitant medications for risk of DDIs, a table of medications that serve as substrate for certain enzyme isoforms inhibited by CardiolRx™ has been prepared (Appendix 17.10).

9.2.12 Laboratory tests

9.2.12.1 Local laboratory tests

Local laboratory tests include CBC, AST/ALT, alkaline phosphatase, bilirubin, creatinine/eGFR, INR, glucose, total cholesterol, lymphocyte count and LDH as well as a serum pregnancy test (beta-hCG, female patients of child bearing potential and at baseline only).

Please see Appendix 17.2.2 for the exact schedule of all laboratory tests.

9.2.12.2 Additional laboratory tests

In addition to local laboratory tests, frozen samples will be retained for the following tests to be analyzed by a central laboratory: hs-troponin, NT-proBNP, D-dimer, hs-CRP, ferritin, TNF-alpha, IL-1 beta, IL-6, IL-10, as well as CBD levels and additional parameters of interest. **These will not be used for genetic testing.**

Please see Appendix 17.2.2 for the exact schedule of all laboratory tests.

All samples will be stored at -70°C at the sites and will be shipped to the Central Laboratory in batches.

9.2.13 Cardiac magnetic resonance imaging (CMR)

A subset of patients at selected sites will undergo a CMR at Day 28. The standardized examination protocol (Appendix 17.11) will include LVEF, LVEDV, LVESV, LAESV, ECV, GLS, LV mass, LGE extent and edema. All images will be analyzed at a Central CMR Core Laboratory.

9.2.14 Management of AEs

9.2.14.1 AE Reporting

An AE is defined as any new untoward medical occurrence or worsening of a pre-existing medical condition in a patient or clinical investigation subject administered an investigational (medicinal) product and that does not necessarily have a causal relationship with this

treatment. An AE can therefore be any unfavorable and unintended sign (including an abnormal laboratory finding, for example), symptom, or disease temporally associated with the use of an investigational product, whether or not considered related to the investigational product.

AEs can be spontaneously reported or elicited during open-ended questioning, examination, or evaluation of a patient. (In order to prevent reporting bias, patients should not be questioned regarding the specific occurrence of one or more AEs.)

Any AE that results in any of the following outcomes will be considered an SAE:

1. Death
2. Life-threatening situation (Patient was at risk of death at the time of the event. This does not refer to an event that might have caused death if it was of greater intensity.)
3. New in-patient hospitalization or prolongation of existing index hospitalization
4. Persistent or significant disability or incapacity
5. Congenital anomaly or birth defect
6. Important medical events that may not result in death, be life-threatening, or require hospitalization but may jeopardize the patient and may require medical or surgical intervention to prevent one of the above outcomes (based upon appropriate medical judgment), e.g., allergic bronchospasm requiring intensive treatment in an emergency room or at home, blood dyscrasias or convulsions that do not result in in-patient hospitalization, or the development of drug dependency or drug abuse. Potential DILI is also considered an important medical event. (See Section 9.2.14.3 for the definition of potential DILI.)

The term “severe” is often used to describe the intensity (severity) of a specific event (as in mild, moderate, or severe pain); the event itself, however, may be of relatively minor medical significance (such as severe headache). By contrast, the term “serious” is used to describe an event based on an event outcome or actions usually associated with events that pose a threat to a patient’s life or functioning. Seriousness (not severity) serves as a guide for defining regulatory reporting obligations.

For all collected SAEs, the clinician who examines and evaluates the patient will determine the event’s causality based on temporal relationship and his/her clinical judgment. The degree of certainty about causality will be graded using the categories below:

Definitely Related: There is clear evidence to suggest a causal relationship, and other possible contributing factors can be ruled out.

Probably Related: There is evidence to suggest a causal relationship, and the influence of other factors is unlikely.

Possibly Related: There is some evidence to suggest a causal relationship. However, the influence of other factors may have contributed to the event.

Unlikely: A clinical event, including an abnormal laboratory test result, whose temporal relationship to drug administration makes a causal relationship improbable and in which other drugs or chemicals or underlying disease provides plausible explanations.

Not related: The SAE is completely independent of study drug administration, and/or evidence exists that the event is definitely related to another etiology.

Pre-existing conditions should be recorded upon patient enrolment (including start date of the condition, and severity - mild, moderate, severe). After the patient signs the informed consent form, any worsening of these conditions would be recorded.

Any new conditions would be recorded including date of onset, date of resolution, severity (mild, moderate, severe, or serious as defined above) and possible relationship to study drug or procedure. As part of the source notes, follow up clinical assessments, laboratory tests, ECGs and diagnostic imaging related to the AE should be documented.

All (S)AEs will be followed until resolved or until a stable condition is reached (as assessed by the Investigator). Follow-up information on patients discontinued from the study due to an SAE must be collected for a minimum period of one (1) month.

9.2.14.2 *Pregnancy*

If, following initiation of the investigational product, it is subsequently discovered that a study patient is pregnant or may have been pregnant at the time of investigational product exposure, including during at least 6 half-lives (18 days) after product administration, the investigational product will be permanently discontinued and the pregnancy will be reported to the Sponsor and the Contract Research Organization (CRO) within 24 hours of the site's awareness of the event. Worldwide Clinical Trials (WWCT) has been contracted as the CRO for this trial. Protocol-required procedures for study discontinuation and follow-up must be performed on the patient unless contraindicated by pregnancy. Other appropriate pregnancy follow-up procedures should be considered if indicated.

9.2.14.3 *Drug-Induced Liver Injury (DILI)*

Wherever possible, timely confirmation of initial liver-related laboratory abnormalities should occur prior to the reporting of a potential DILI event. All occurrences of potential DILIs, meeting the defined criteria below, must be reported as SAEs.

Potential DILI is defined as:

1. ALT or AST elevation $> 8 \times \text{ULN}$

OR
2. ALT or AST elevation $> 5 \times \text{ULN}$ for more than 2 weeks

OR

3. ALT or AST elevation $> 3 \times \text{ULN}$ and bilirubin $> 2 \times \text{ULN}$ or INR > 1.5 .

If a patient meets one of the above criteria, the study drug needs to be discontinued and the assessments of ALT, AST, bilirubin and alkaline phosphatase, as well as a physical examination need to be repeated every 24 hours until all abnormalities have normalized (in the investigator's opinion) or returned to the baseline state.

Elevations in ALT or AST $> 3 \times \text{ULN}$ or bilirubin $> 2 \times \text{ULN}$ alone, i.e., when not concomitant, are not grounds for withdrawal but are to be followed up, as above, within 72 hours of notice of abnormal results.

9.2.14.4 *Overdose*

All occurrences of overdose must be reported as SAEs. An overdose is defined as the accidental or intentional administration of any dose of a product that is considered both excessive and medically important.

9.2.14.5 *Drug-Drug Interactions*

CardiolRx™ is known to be metabolized largely through the cytochrome P450 enzyme system in the liver. A number of the drugs commonly used in the management of cardiovascular or concomitant conditions are also capable of being inducers or inhibitors of these enzymes. The patients should specifically be monitored for (S)AEs that might reflect DDIs. See section 6.3 of the IB for more detailed discussion.

In addition, to aid investigators in screening concomitant medications for risk of DDIs, a table of medications that serve as substrate for certain enzyme isoforms inhibited by CardiolRx™ has been prepared (Appendix 17.10).

9.2.14.6 *Reporting of SAEs*

All SAEs experienced by a patient after informed consent has been obtained must be reported to the Sponsor and WWCT within 24 hours of the site's awareness of the event. A written summary fully documenting the event, in order to permit the Sponsor to file a report which satisfies regulatory guidelines, will follow within three calendar days. The event shall also be reported to the Institutional Review Board (IRB) in accordance with IRB reporting requirements in addition to the FDA and other Health Authorities within the timelines as per regional requirements.

The Sponsor commits to the FDA reporting requirements including:

- Reporting any unexpected fatal or life-threatening suspected adverse reactions to FDA no later than 7 calendar days after initial receipt of the information [21 CFR 312.32(c)(2)].
- Reporting any (1) serious, unexpected suspected adverse reactions, (2) findings from other clinical, animal, or in-vitro studies that suggest significant human risk, and (3) a clinically important increase in the rate of a serious suspected adverse reaction to

PROPRIETARY AND CONFIDENTIAL

this Division and to all investigators no later than 15 calendar days after determining that the information qualifies for reporting [21 CFR 312.32(c)(1)].

- Submitting annual progress reports within 60 days of the anniversary of the date that the IND became active (the date clinical studies were permitted to begin) [21 CFR 312.33].

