6.7.1 Permanent Suspension of Study Treatment

The investigator may permanently suspend the treatment in the following cases:

- If the patient's QTc interval is > 500 msec or an increase from baseline of > 60 msec is observed (please refer to section 9.2.3 for BBB correction);
- A DDI is identified with a concomitant medication that is medically required and cannot be resolved without the discontinuation of the study medication;

- If, in the view of the investigator, the patient experiences a severe allergic reaction that cannot be explained by the administration of any other medication;
- Development of liver function abnormality, as described in section 9.2.14.3.
- Development of an AE or any medical condition, which, in the opinion of the investigator, necessitates permanent suspension of study treatment;
- Withdrawal of consent.
- If the blind is broken (only allowed in emergency situations to determine appropriate patient care)

Patients have the right to discontinue study treatment for any reason. However, unless they withdraw consent and are no longer willing to participate, they should be followed for the remainder of the trial and all (S)AEs should be reported, regardless of whether or not the event is of CV origin or occurs under the care of another physician or institution.

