8 INVESTIGATIONAL PRODUCTS, DOSE AND DURATION OF TREATMENT

8.1 *Investigational Product*

CardiolRx™ is pharmaceutically produced. It contains cannabidiol in a concentration of 100 mg/ml and is free of tetrahydrocannabinol (THC; <5 ppm).

8.2 *Administration, Dosage and Duration of Treatment*

Study drug will be administered orally (via syringe)* with food according to the following treatment schedule:

Study Day	a.m. dose [mg/kg of body weight]	p.m. dose [mg/kg of body weight]
	CardiolRx™ or placebo	CardiolRx™ or placebo
1	N/A	2.5
2	2.5	2.5
3	2.5	5
4	5	5
5	5	7.5
6 - 28	7.5	7.5

At each study visit, drug accountability will be done. New bottles of study medication will be dispensed at each study visit (Days 3, 5, 7, 14 and 21).

If the next higher dose is not tolerated, the patient should return to the last tolerated dose. The highest tolerated dose will be administered until Day 28 (4 weeks post randomization).

The maximum treatment period will be 28 days.

* If the patient requires mechanical ventilation, the study medication is administered through a naso-gastric tube.

Justification for Dosing Regimen

COVID-19 is an acute illness with, at times, rapid progression of symptoms and signs. Because of this, it seems important to increase the blood level of the investigational agent as quickly as possible to achieve the potential anti-inflammatory and anti-cytokine actions that are likely to be important in this population. However, this agent has not been administered previously to this population, so care must be taken to observe closely for

adverse drug effects or drug-drug interactions that might have significant negative consequences. A similar product containing a highly purified botanical extract of CBD has been approved for use in pediatric epilepsy to a dose up to 10 mg/kg twice daily (Devinsky et al. 2016). We have chosen to restrict the maximum dose in this COVID-19 population to 7.5 mg/kg b.i.d. because of the expected elderly and perhaps frail condition of some of the enrolled patients. Investigators are encouraged to decrease the dose if there are indications of intolerance of a given dose to the previously tolerated dose.

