- Study drug dose adjustment to 7.5 mg/kg b.i.d., if 5.0 mg/kg b.i.d. is well-tolerated (If 5.0 mg/kg b.i.d. is not tolerated, then dose decrease back to 2.5 mg/kg b.i.d.)
- Study drug accountability
- Retention of frozen samples for hs-troponin, NT-proBNP, d-dimer, hs-CRP, ferritin, TNF-alpha, IL-1 beta, IL-6, IL-10 and additional parameters of interest
- Retention of frozen samples for CBD levels

Day 7

- Clinical assessment
- Vital signs, including HR, blood pressure and weight
- 12-lead ECG, including QTc interval assessment 5 hours post morning dose (time window 3.5 – 6 hours)
- Assessment of Ordinal Outcome Scale
- AE and SAE recording
- Recording of changes in concomitant medications
- Study drug dose adjustment and accountability
- Local laboratory assessments, including CBC, AST/ALT, alkaline phosphatase, bilirubin, creatinine/eGFR, INR, lymphocyte count and LDH
- Retention of frozen samples for hs-troponin, NT-proBNP, D-dimer, hs-CRP, ferritin, TNF-alpha, IL-1 beta, IL-6, IL-10 and additional parameters of interest
- Retention of frozen samples for CBD levels

If the patient is discharged before Day 7, the assessments up to Day 7 will be carried out as out-patient or home visits. After Day 7, all remaining scheduled assessments will be carried out during out-patient visits.

Time windows for out-patient visits or home visits up to Day 7 are +/- 1 day; after Day 7, time windows are +/- 2 days.

Day 14

- Clinical assessment
- Vital signs, including HR, blood pressure and weight
- 12-lead ECG, including QTc interval assessment 5 hours post morning dose (time window 3.5 – 6 hours)
- Assessment of Ordinal Outcome Scale

- AE and SAE recording
- Recording of changes in concomitant medications
- Study drug dose adjustment and accountability
- Local laboratory assessments, including CBC, AST/ALT, alkaline phosphatase, bilirubin, creatinine/eGFR, INR, lymphocyte count and LDH

Day 21

- Clinical assessment
- Vital signs, including HR, blood pressure and weight
- 12-lead ECG, including QTc interval assessment 5 hours post morning dose (time window 3.5 – 6 hours)
- Assessment of Ordinal Outcome Scale
- AE and SAE recording
- Recording of changes in concomitant medications
- Study drug dose adjustment and accountability

Day 28

- Clinical assessment
- Vital signs, including HR, blood pressure and weight
- Chest X-ray
- 12-lead ECG, including QTc interval assessment 5 hours post morning dose (time window 3.5 – 6 hours)
- LVEF by echocardiography

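### The liver follow-up panel for patients kept on drug with isolated ALT/AST >3x ULN omits INR, although INR >1.5 would then require stopping; against a retest 3 days after the finding draw, this delays the next INR by about 4 or 11 nominal days

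*Protocol*

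**What the plan says.** Protocol Section 9.2.14.3 defines potential DILI in three ways:

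1. ALT or AST >8x ULN.
2. ALT or AST >5x ULN lasting more than 2 weeks.
3. ALT or AST >3x ULN together with bilirubin >2x ULN or INR >1.5.

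Meeting any of these requires discontinuation and an SAE report. Section 6.7.1 lists "Development of liver function abnormality, as described in section 9.2.14.3" among the reasons for permanent suspension.

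Once a criterion is met, "the assessments of ALT, AST, bilirubin and alkaline phosphatase, as well as a physical examination need to be repeated every 24 hours" until the abnormalities resolve or return to baseline. INR is not in that list. Isolated rises in ALT/AST >3x ULN, or in bilirubin >2x ULN, "are not grounds for withdrawal but are to be followed up, as above, within 72 hours of notice of abnormal results".

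INR is otherwise part of the scheduled local laboratory set. Section 9.1 includes it at baseline and repeats this line on Days 7, 14 and 28: "Local laboratory assessments, including CBC, AST/ALT, alkaline phosphatase, bilirubin, creatinine/eGFR, INR, lymphocyte count and LDH". Day 21 has a visit but no laboratory tests. On timing, Section 9.1 says "Time windows for out-patient visits or home visits up to Day 7 are +/- 1 day" and "after Day 7, time windows are +/- 2 days". Section 8.2 limits dosing: "The maximum treatment period will be 28 days".

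Two other places bear on the point. Section 9.2.14.1 says that "follow up clinical assessments, laboratory tests, ECGs and diagnostic imaging related to the AE should be documented". Appendix 17.10 advises monitoring INR in patients taking warfarin.

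**The concern.** The follow-up of an isolated transaminase rise has two purposes: to see whether it settles, and to see whether the patient has crossed into a category that requires stopping. The stated panel serves the second purpose for every route into potential DILI except INR. A patient can stay on drug under this follow-up, have every listed test repeated on time, and still meet criterion 3 through INR without the protocol prompting anyone to look.

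What is at stake is patient safety and the working of the plan's own stopping rule. The matter does not touch the primary endpoint, the sample size or the planned comparisons.

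**Working it through.** The plan states no figure for this interval, so there is none to reproduce. The check sets the triggers against the panel and then takes differences between scheduled INR days.

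**Step 1: triggers against the repeat panel (Section 9.2.14.3)**

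| Route to mandatory stop | Tests needed | In the panel? |
|---|---|---|
| Criterion 1 | ALT, AST | Yes |
| Criterion 2 | ALT, AST over time | Yes |
| Criterion 3, bilirubin arm | ALT, AST, bilirubin | Yes |
| Criterion 3, INR arm | ALT, AST, INR | INR missing |

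Criterion 3 has no brackets. On the natural reading, INR >1.5 counts only alongside ALT/AST >3x ULN. If it were read as standing alone, INR would still be a trigger and the panel would still omit it.

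**Step 2: interval on drug to the next scheduled INR**

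Interval = day of next scheduled INR − day of the draw that found the rise.

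- Found at Day 7: 14 − 7 = 7 nominal days.
- Found at Day 14: 28 − 14 = 14 nominal days, because Day 21 has no laboratory tests.

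With the Section 9.1 windows:

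- Day 7 as an out-patient or home visit (±1 day), Day 14 ±2 days: 12 − 8 = 4 to 16 − 6 = 10 days.
- Day 7 in hospital (no window stated, so taken as Day 7 itself): 12 − 7 = 5 to 16 − 7 = 9 days.
- Day 14 to Day 28: minimum 26 − 16 = 10 days; maximum on drug 28 − 12 = 16 days. Visit to visit the maximum is 30 − 12 = 18, but dosing ends on Day 28.

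**Step 3: delay caused by the omission**

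The draw that found the rise already included an INR, and even a panel with INR would be repeated only within 72 hours of notice. Taking the retest as 3 days after the draw:

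- Day 7 finding: 7 − 3 = 4 nominal days (4 − 3 = 1 to 10 − 3 = 7 with out-patient or home windows; 5 − 3 = 2 to 9 − 3 = 6 in hospital).
- Day 14 finding: 14 − 3 = 11 nominal days (10 − 3 = 7 to 16 − 3 = 13 with windows).

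The 3 days are an assumption. A retest 1 day after the draw gives 7 − 1 = 6 and 14 − 1 = 13 days. Because the 72 hours run from notice, a late report can push the retest later and shorten the delay. The figures describe a patient whose INR is already above 1.5 at the retest. If INR crosses later, the gain from the fix depends on whether the daily repetition carries over to isolated rises, which the text does not settle.

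**Step 4: who is in the missed case**

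All of the following must hold: INR newly >1.5 since the last scheduled draw; ALT/AST still >3x ULN without meeting criterion 1 or 2; bilirubin at or below 2x ULN; and no discretionary INR. The documents give no rate for any of these.

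**The case against.** The strongest reply is that the list is not clearly exhaustive and that ordinary care fills the gap. Section 9.2.14.1 requires adverse events to be followed until resolved or stable, and an abnormal laboratory finding can be an adverse event. The panel itself runs until the abnormalities resolve, which cannot be judged without an INR if INR was one of them. The investigator may order an INR or suspend treatment at any time. Patients are also seen: Day 21 has a clinical assessment, vital signs and an ECG. This stands as mitigation. None of it requires an INR when the last one was normal, and that is the case in question.

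A second reply concerns size. A reader might infer that the omission leaves INR unchecked for the whole 7 or 14 days. The documents do not support that as its effect, because the interval starts with a same-day INR and the fix would bring the next one forward only to the retest. The attributable delay is the smaller figure in Step 3.

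A reader might also infer that no text anywhere prompts an INR between scheduled visits, or that liver monitoring as a whole is inadequate. Neither follows. Appendix 17.10 prompts INR monitoring in warfarin users, though as interaction advice outside the liver rule, and the other routes to stopping stay under repeat testing.

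A third reply is that more INR testing has consequences. Anticoagulants are not excluded, and Section 3.5 describes anticoagulation as given on deterioration. Under Section 9.2.14.3, an INR >1.5 caused by an anticoagulant in a patient with ALT/AST >3x ULN would mean discontinuation and an SAE report, not just a result to interpret. This stands and belongs in the cost, although the same result at a scheduled visit already has that consequence.

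**Conclusion.** The point holds as a minor patient-safety defect in a stated rule: the follow-up panel cannot detect one of the plan's own mandatory stopping criteria. Its size is a delay of about 4 nominal days after a Day 7 finding and 11 after a Day 14 finding, assuming a retest 3 days after the draw. It rests on reading *as above* as the panel just before it, which is the only follow-up described there.

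These are lengths of time, not numbers of patients. A reader might infer that patients were harmed or that results are affected. The documents support neither: the frequency cannot be derived, and nothing here bears on an endpoint or on power. SAP Section 2 records that the study was terminated early, so the correction is useful mainly if this liver section is reused.

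**What to change.** In Section 9.2.14.3, define the repeat panel as ALT, AST, bilirubin, alkaline phosphatase, INR and a physical examination. State that it applies both to potential DILI and to the 72-hour follow-up of isolated elevations. Leave the INR >1.5 threshold unchanged.

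The cost is a wording change in one section and one local INR per repeat, which becomes daily if the 24-hour frequency is meant to carry over. INR is already a local test in this trial. The documents do not say whether the repeat chemistry sample can also serve for INR, so a separate tube may be needed. The main downside is that in anticoagulated patients an INR >1.5 found at the retest would trigger discontinuation and SAE reporting under the existing criterion, as it already would at a scheduled visit. Whether such patients need an exception is a separate question about the criterion itself.
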